10.3 POPULATIONS FOR ANALYSIS

As a modified intention to treat analysis we will report data on participants who received at least one dose of ibrutinib.

10.4 STATISTICAL ANALYSIS

10.4.1 General approach

The proportion of evaluable participants who experience a response will be reported along with a confidence interval.

10.4.2 Analysis of the primary endpoints

The fraction of evaluable participants who experience a response will be determined and reported along with 80% and 95% two-sided confidence intervals.

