10.2 SAMPLE SIZE DETERMINATION

The primary objective of this trial is to determine the overall response rate of ibrutinib as a first-line treatment for subjects with newly diagnosed chronic GvHD based on the response at or before 6 months, according to the 2014 NIH Consensus Criteria. In similar subjects who ordinarily would receive steroid treatment, the clinical response rate using NIH criteria may typically be on the order of 30-40%. The goal would be to determine if using ibrutinib would rule out a 20% response rate and target a rate of 45%. For these subjects, the trial will be conducted using an optimal two-stage phase II trial design (Simon R, Controlled Clinical Trials 10:1-10, 1989) in order to rule out an unacceptably low PR+CR rate of 20% ($p_0=0.20$) in favor of an improved response rate of 45% ($p_1=0.45$). With $\alpha=0.10$ (probability of accepting a poor treatment=0.10) and $\beta = 0.10$ (probability of rejecting a good treatment=0.10), this first stage will enroll 14 evaluable subjects, and if 0 to 3 of the 14 have a clinical response, then no further subjects will be accrued. If 4 or more of the first 14 subjects have a response, then accrual would continue until a total of 25 evaluable subjects have been enrolled. As it may take 3 to 6 months to determine if a subject has experienced a response, a temporary pause in the accrual may be necessary to ensure that enrollment to the second stage is warranted. If there are 4 to 7 subjects with a response out of 25 subjects, this would be an uninterestingly low response rate. If there were 8 or more of 25 (32%) who experienced a response, this would be sufficiently interesting to warrant further study in later trials. Under the null hypothesis (20% response rate), the probability of early termination is 69.8%.

It is expected that approximately 1-2 subjects per month may enroll on this trial; thus, it is anticipated that 1.5 to 2 years may be required for accrual of up to 25 evaluable subjects. In order to allow for up to 3 inevaluable subjects and screen failures (screening will occur on this protocol), the accrual ceiling will be set at 40 (3 for inevaluable participants and 12 for screen failures).

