10.4.3 Analysis of the secondary endpoints

- To evaluate safety of ibrutinib for newly diagnosed chronic GvHD
- To evaluate Failure Free Survival

The secondary objectives will each be evaluated using standard statistical methods, which will largely consist of reporting descriptive statistics and associated 95% confidence intervals. Time to event endpoints such as failure free survival will be determined using a Kaplan-Meier curve.

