10.4.6 Planned interim analyses

As indicated in the sample size determination section, an interim evaluation of the number of participants who experienced a success in the first stage of the two-stage optimal design will be performed to ensure that enrollment to the second stage is warranted.

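### Does the primary analysis need a named confidence interval method when only 14 or 25 participants are analysed?

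*Combined protocol and SAP*

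**What the plan says.** Section 10.4.1 gives the general approach: "The proportion of evaluable participants who experience a response will be reported along with a confidence interval". Section 10.4.2 makes this specific for the primary endpoint: the fraction with a response will be "determined and reported along with 80% and 95% two-sided confidence intervals". Section 10.4.3 handles the secondary objectives by standard methods, "which will largely consist of reporting descriptive statistics and associated 95% confidence intervals". None of these sections names an exact, Wilson, Wald or two-stage-adjusted interval.

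The decisions are defined elsewhere, by counts. Section 10.2 sets a Simon optimal two-stage design: stop if 3 or fewer of the first 14 evaluable participants respond, otherwise continue to 25. The final criterion reads "If there were 8 or more of 25 (32%) who experienced a response, this would be sufficiently interesting". Section 10.4.6 confirms that the interim look is a count as well: "an interim evaluation of the number of participants who experienced a success in the first stage of the two-stage optimal design will be performed".

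**The concern.** The two intervals are the only measure of uncertainty that Section 10.4.2 promises for the primary result. In large samples the common methods agree and the choice hardly matters. With 14 or 25 participants they do not agree. A Wald interval can have a negative lower limit or zero width, and it often covers the true rate less often than its label says. The text as written does not exclude it.

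There is also a question of how the result looks at the success boundary. The design's error rate of 0.10 is one-sided, so a two-sided 80% interval is what a reader would naturally compare with the 20% null rate. At 8 of 25, whether that interval contains 20% depends on the method. If the method were chosen after the data were seen, the presentation could be chosen with it.

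**Working it through.** **Inputs.** From Section 10.2: first-stage size 14, stop at 3 or fewer responses, total 25, success at 8 or more, null rate 0.20, target 0.45, both error rates 0.10, early termination 69.8% under the null. From Section 10.4.2: two-sided levels of 80% and 95%.

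**Step 1: reproduce the design.** Let X₁ ~ Bin(14, p) and X₂ ~ Bin(11, p).
- Early termination: P(X₁ ≤ 3) at p = 0.20 is 0.698, which matches the stated 69.8%.
- Success: P(X₁ ≥ 4 and X₁ + X₂ ≥ 8) is 0.0933 at p = 0.20 (limit 0.10) and 0.9026 at p = 0.45 (at least 0.90 required).

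The stated design reproduces.

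**Step 2: coverage under the actual two-stage sampling.** For each method, coverage at a true rate p is the sum of two parts:
- P(X₁ = x) over x = 0 to 3 for which the interval from x/14 contains p;
- P(X₁ ≥ 4, X₁ + X₂ = t) over t = 4 to 25 for which the interval from t/25 contains p.

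The minimum and mean below are over true rates 0.20 to 0.50 in steps of 0.001.

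| Method | Level | p = 0.20 | p = 0.45 | Minimum | Mean |
|---|---|---|---|---|---|
| One-sample exact | 80% | 0.913 | 0.807 | 0.799 | 0.861 |
| Wald | 80% | 0.709 | 0.751 | 0.654 | 0.751 |
| Wilson | 80% | 0.863 | 0.751 | 0.697 | 0.781 |
| One-sample exact | 95% | 0.983 | 0.964 | 0.954 | 0.972 |
| Wald | 95% | 0.939 | 0.883 | 0.798 | 0.900 |
| Wilson | 95% | 0.957 | 0.956 | 0.905 | 0.950 |

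As an example of where the figures come from, at p = 0.45 the Wald 95% interval contains 0.45 only for totals of 7 to 15 of 25, and for no first-stage stop. The exact interval contains it for 3/14 and for 6 to 16 of 25.

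The exact interval is safe but conservative. At the null rate its 80% version over-covers by 0.913 − 0.80 = 0.113, while Wald under-covers by 0.80 − 0.709 = 0.091. The exact interval is not strictly guaranteed here either, because the one-sample calculation ignores the interim stop. It falls to 0.799 at the 80% level within this range, and to 0.949 at the 95% level near a true rate of 0.536, just outside it. Both dips are negligible.

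**Step 3: the boundary result, 8/25 = 0.32.**
- Wald: the standard error is √(0.32 × 0.68 / 25) = 0.0933. The 80% interval is 0.32 ± 1.2816 × 0.0933 = 0.200 to 0.440 (lower limit 0.2004). The 95% interval is 0.32 ± 1.96 × 0.0933 = 0.137 to 0.503.
- One-sample exact 80%: solving P(X ≥ 8) = 0.10 and P(X ≤ 8) = 0.10 for X ~ Bin(25, p) gives 0.196 to 0.467. The 95% interval is 0.149 to 0.535.
- Wilson 80%: 0.215 to 0.447.
- Exact with stagewise ordering, 80%: 0.203 to 0.477. It excludes 20% because it uses the design's own tail probability, 0.0933 at p = 0.20.

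So Wald, Wilson and two-stage exact exclude 20% at the 80% level, and only the one-sample exact interval includes it. Between the two exact methods, the disagreement about 20% is confined to the 80% interval at this one result. The probability of observing exactly 8/25 is 0.050 at a true rate of 0.20, 0.132 at 0.30 and 0.056 at 0.45.

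**Step 4: does any decision move?** No. Stopping at 3 or fewer of 14, continuing at 4 or more, and success at 8 or more of 25 are all defined without reference to an interval.

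**The case for a change.** The case for naming a method is fair. It would take a few words, need no extra data, and remove any freedom to choose after the results are known. The differences can also show. At 3/14 the 95% upper limit is 0.508 exact but 0.429 Wald, so Wald would appear to exclude the 45% target and exact would not. At 0/14 the Wald interval collapses to 0 to 0, against 0 to 0.232 exact at the 95% level. Averaged over true rates 0.20 to 0.50, a Wald 95% interval covers only 90.0%.

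These figures stand, and naming the method would be tidy. They do not show a fault in the plan, for two reasons. First, the shortfall arises only if the analyst picks the weakest common option for a small binomial sample. Nothing in the documents points that way, and the design itself is built on exact binomial probabilities. Second, the obvious choice is not free of drawbacks. The one-sample exact interval over-covers and, at the minimum success, includes the rate being ruled out, so it would need an added note that the count rule governs. The stagewise exact interval agrees with that rule but has much wider upper limits below it: at 4/25 the 95% upper limit is 0.508 against 0.361. Wilson is closest to its label on average and dips below it at some rates. Choosing among these is a trade-off on which statisticians reasonably differ.

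**Conclusion.** No change to the plan follows. Sections 10.4.1 to 10.4.3 do leave the interval method open, and a Wald interval would be a poor way to fill the gap: mean coverage over true rates 0.20 to 0.50 is 0.751 for a labelled 80% and 0.900 for a labelled 95%. But this is missing detail that a competent analyst supplies as a matter of course. The exact, two-stage exact and Wilson intervals are all defensible, each with its own cost. Stating the chosen method beside the result in the report tells the reader what is needed. The interim and final decisions rest on counts and are unaffected.

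The coverage figures assume that exactly 14 or 25 evaluable participants are analysed, as in Section 10.2. Section 3.1 speaks of at least 25 and up to 28, and other denominators would shift the figures. For example, at 8/28 the exact 80% interval is 0.174 to 0.422. That would not alter the conclusion about the unnamed method.

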10.4.3 Analysis of the secondary endpoints

- To evaluate safety of ibrutinib for newly diagnosed chronic GvHD
- To evaluate Failure Free Survival

The secondary objectives will each be evaluated using standard statistical methods, which will largely consist of reporting descriptive statistics and associated 95% confidence intervals. Time to event endpoints such as failure free survival will be determined using a Kaplan-Meier curve.

10.4.4 Safety analyses

Safety of the agent will be assessed by determining the grade of adverse events noted in each participant, and reporting the fraction with grade 3 and grade 4 adverse events. Participants who receive at least one dose of the study treatment will be evaluable for safety. Safety data will be presented in a summary. The safety data will consist of the reporting of all adverse events, and may also include reporting vital signs, physical examination data, and laboratory safety data.

10.4.5 Baseline descriptive statistics

Limited demographic and clinical characteristics of all participants will be reported.

10.4.6 Planned interim analyses

As indicated in the sample size determination section, an interim evaluation of the number of participants who experienced a success in the first stage of the two-stage optimal design will be performed to ensure that enrollment to the second stage is warranted.

10.4.7 Subgroup analyses

None are intended.

10.4.8 Tabulation of individual participant data

No individual participant data is intended to be reported.

10.4.9 Exploratory analyses

The following are the intended exploratory objectives:

- To evaluate chronic GvHD response rate at 6 weeks, 3 months, 9 months, and 1 year
- To evaluate the duration of chronic GvHD response
- To evaluate ability to taper steroids and other systemic immunosuppression
- To evaluate need for steroid pulses
- To evaluate the need for therapy change
- To evaluate subject reported outcome by Lee Symptom Scale
- To evaluate subject reported outcome by SF36

- To evaluate subject reported outcome by the NIH Chronic GvHD Activity Assessment-Patient Self Report-Form B
- To monitor for recurrence of the original malignancy or development of new cancers
- To evaluate changes in T and B regulatory and effector subsets, in patterns of gene expression and in proposed plasma biomarkers to correlate these changes with clinical assessments of chronic GVHD

The Lee scale results, SF36 results, and NIH cGVHD activity assessment form B results after treatment will be compared to the pre-treatment results using a Wilcoxon signed rank test. Any exploratory evaluations which generate quantitative measures will be done using descriptive statistics including confidence intervals when appropriate. Any statistical tests performed for evaluation of exploratory objectives will be done without formal adjustment for multiple comparisons, but in the context of the number of tests performed.

11 COLLABORATIVE AGREEMENTS

11.1 COOPERATIVE RESEARCH AND DEVELOPMENT AGREEMENT (CRADA)

This study will be conducted under a Collaborative Research and Development Agreement (CRADA) with Pharmacyclics LLC and Washington University in St. Louis (#03211).

11.2 MULTI-INSTITUTIONAL GUIDELINES

Until an electronic submission system is available to participating sites, documents requiring submission to the reviewing IRB per reliance agreement, including local consent documents generated from an approved model consent, should be provided to the coordinating center for submission to the IRB. Thereafter, consents may be submitted directly to the IRB using iRIS.

12 HUMAN SUBJECTS PROTECTIONS

12.1 RATIONALE FOR SUBJECT SELECTION

No subjects will be excluded from participation based on gender, race or ethnicity. The study will be open to all subjects who satisfy the inclusion criteria and provide an informed consent to the protocol.

12.2 PARTICIPATION OF CHILDREN

As there is no experience with ibrutinib in children, this study will be limited to subjects age 18 years or older.

12.3 PARTICIPATION OF SUBJECTS UNABLE TO GIVE CONSENT

12.3.1 NCI

Adults unable to give consent are excluded from enrolling in the protocol. However, re-consent may be necessary and there is a possibility, though unlikely, that subjects could become decisionally impaired. For this reason and because there is a prospect of direct benefit from research participation (section **Error! Reference source not found.**), all subjects \geq age 18 will be offered the opportunity to fill in their wishes for research and care, and assign a substitute decision maker on the “NIH Advance Directive for Health Care and Medical Research Participation” form so that another person can make decisions about their medical care in the event that they become incapacitated or cognitively impaired during the course of the study.

Note: The PI or AI will contact the NIH Ability to Consent Assessment Team (ACAT) for evaluation to assess ongoing capacity of the subjects and to identify an LAR, as needed..

Please see Section **12.5.1** for consent procedure.

12.3.2 Participating Sites

Participating sites relying on the NIH IRBO should follow local policies for assessing capacity.

Please see Section **12.5.1** for consent procedure.

12.4 RISK/BENEFIT ASSESSMENT

12.4.1 Known Potential Risks

12.4.1.1 Related to Ibrutinib

Potential risks of ibrutinib include the range of toxicities described above, in drug insert, investigational brochure and the consent form. There may also be unexpected side effects. All subjects will be carefully monitored for side effects.

12.4.1.2 Related to Blood Collection

Minor complications including bleeding, pain, and hematoma formation at the site of blood draws, or infections may rarely occur. Up to approximately 135mL of blood will be collected during one visit and no more than 300mL will be collected over an 8-week period.

12.4.1.3 Related to Tissue Biopsy

Skin or oral mucosa biopsy are minor surgical procedures that may be associated with temporary bleeding, hematoma at the site, local infection and postoperative discomfort. These risks are small (generally < 5%) and transient. All bone marrow biopsies on the study will be done only as a part of routine care, and not study-mandatory.

12.4.1.4 Related to Questionnaires

The potential risk of questionnaires include questions that may be sensitive in nature.

12.4.2 Known Potential Benefits

The potential benefit is decreased symptoms that are caused by the cGVHD.

12.4.3 Assessment of Potential Risks and Benefits

Preclinical results demonstrate a substantial therapeutic benefit of ibrutinib treatment to reduce the prolonged effects of chronic GvHD with an acceptable safety profile. Therefore, the benefits outweigh the risks that the participants are exposed to.

12.5 CONSENT PROCESS AND DOCUMENTATION

The informed consent document will be provided as a physical or electronic document to the participant or consent designee(s) as applicable for review prior to consenting. A designated study investigator will carefully explain the procedures and tests involved in this study, and the associated risks, discomforts and benefits. In order to minimize potential coercion, as much time as is needed to review the document will be given, including an opportunity to discuss it with friends, family members and/or other advisors, and to ask questions of any designated study investigator. A signed informed consent document will be obtained prior to entry onto the study.

The initial consent process as well as re-consent, when required, may take place in person or remotely (e.g., via telephone or other site approved remote platforms used in compliance with site policies) per discretion of the designated study investigator and with the agreement of the participant/consent designee(s). Whether in person or remote, the privacy of the subject will be maintained. Consenting investigators (and participant/consent designee, when in person) will be located in a private area (e.g., clinic consult room). When consent is conducted remotely, the participant/consent designee will be informed of the private nature of the discussion and will be encouraged to relocate to a more private setting if needed.

Consent will be documented with required signatures on the physical document (which includes the printout of an electronic document sent to participant) or as described below, with a manual (non-electronic) signature on the electronic document. When required, witness signature will be obtained similarly as described for the investigator and participant.

Manual (non-electronic) signature on electronic document:

When a manual signature on an electronic document is used for the documentation of consent at the NIH Clinical Center, this study will use the following to obtain the required signatures:

- Adobe platform (which is not 21 CFR Part 11 compliant); or,
- iMedConsent platform (which is 21 CFR Part 11 compliant)

During the consent process, participants and investigators will view individual copies of the approved consent document on screens at their respective locations (if remote consent); the same screen may be used when in the same location but is not required.

Both the investigator and the participant will sign the document using a finger, stylus or mouse.

Note: Refer to the CCR SOP PM-2, Obtaining and Documenting the Informed Consent Process for additional information (e.g., verification of participant identity when obtaining consent remotely) found at:

<https://ccrod.cancer.gov/confluence/pages/viewpage.action?pageId=73203825>.

The above is for NIH. Please see site specific supplement for electronic signature requirements for participating site (i.e., Wash U).

12.5.1 Consent Process for Adults Who Lack Capacity to Consent to Research Participation

For participants addressed in Section **12.3** an LAR will be identified consistent with Policy 403 and informed consent obtained from the LAR, as described in Section **12.5**.

13 REGULATORY AND OPERATIONAL CONSIDERATIONS

13.1 STUDY DISCONTINUATION AND CLOSURE

This study may be temporarily suspended or prematurely terminated if there is sufficient reasonable cause. Written notification, documenting the reason for study suspension or termination, will be provided by the suspending or terminating party to study participants, investigators, funding agency, the Investigational New Drug (IND) sponsor and regulatory authorities. If the study is prematurely terminated or suspended, the Principal Investigator (PI) will promptly inform study participants, the Institutional Review Board (IRB), and sponsor and will provide the reason(s) for the termination or suspension. Study participants will be contacted, as applicable, and be informed of changes to study visit schedule.

Circumstances that may warrant termination or suspension include, but are not limited to:

- Determination of unexpected, significant, or unacceptable risk to participants
- Demonstration of efficacy that would warrant stopping
- Insufficient compliance to protocol requirements
- Data that are not sufficiently complete and/or evaluable
- Determination that the primary endpoint has been met
- Determination of futility

Study may resume once concerns about safety, protocol compliance, and data quality are addressed, and satisfy the sponsor, IRB and as applicable, Food and Drug Administration (FDA).

13.2 QUALITY ASSURANCE AND QUALITY CONTROL

Each clinical site will perform internal quality management of study conduct, data and biological specimen collection, documentation and completion. An individualized quality management plan will be developed to describe a site's quality management.

Quality control (QC) procedures will be implemented beginning with the data entry system and data QC checks that will be run on the database will be generated. Any missing data or data anomalies will be communicated to the site(s) for clarification/resolution.

Following written Standard Operating Procedures (SOPs), the monitors will verify that the clinical trial is conducted and data are generated and biological specimens are collected, documented (recorded), and reported in compliance with the protocol, International Conference on Harmonisation Good Clinical Practice (ICH GCP), and applicable regulatory requirements (e.g., Good Laboratory Practices (GLP), Good Manufacturing Practices (GMP)).

The investigational site will provide direct access to all trial related sites, source data/documents, and reports for the purpose of monitoring and auditing by the sponsor, and inspection by local and regulatory authorities.

13.3 CONFLICT OF INTEREST POLICY

The independence of this study from any actual or perceived influence, such as by the pharmaceutical industry, is critical. Therefore, any actual conflict of interest of persons who have a role in the design, conduct, analysis, publication, or any aspect of this trial will be disclosed and managed. Furthermore, persons who have a perceived conflict of interest will be required to have such conflicts managed in a way that is appropriate to their participation in the design and conduct of this trial. The study leadership in conjunction with the National Cancer Institute has established policies and procedures for all study group members to disclose all conflicts of interest and will establish a mechanism for the management of all reported dualities of interest.

